**D. 4d4. Power and sample size:**

Small facilities will have limited power to detect small implementation effects, and evaluating implementation success for these sites will incorporate mixed methods also using qualitative findings. The ability to pool sites using

**Table 6.** Power calculation

Estimated Number of At-Risk Veterans in Post-Implementation Period	50	75	200	750
Effect size (with power=0.80)	0.40	0.32	0.20	0.10

similar implementation strategies will ensure our evaluation has adequate power. **Table 6** highlights that post-implementation follow-up periods that include samples of 200 patients will allow for detection of meaningful effect sizes in the 0.2 range.

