**D.4d. Quantitative evaluation:**

**D.4d1. Cohort identification:** To assess impact of IF efforts, we will identify a cohort of at-risk patients—those who have OUD but are not prescribed MOUD—to track their outcomes over time. Methods to identify at-risk patients will be harmonized across all implementation sites. These will include use of available data in the Corporate Data Warehouse (CDW), including medication/pharmacy records (inpatient and outpatient), toxicology screen results, primary care and mental health care utilization, inpatient admissions, comorbidity data, recent treatment and service use such as alternative pain treatments for the subgroup of MOUD patients with pain, and other information to determine at-risk Veterans appropriate for referral for MOUD. We will compare outcomes at each implementation site during the post-implementation period to outcomes prior to implementation, using each site as their own control. Each site will have a defined implementation start date and an implementation start-up period of 3-months in which outcomes will not be attributed to either the pre- or post-implementation period. For sites that have booster or additional implementation efforts, additional start dates of those efforts will be tracked. Harmonization of definitions for at-risk Veterans will also facilitate comparing sites across VHA not participating in MOUD-related implementation activities to examine secular trends and to rapidly identify targets for expanding the implementation efforts for MOUD referral in additional VISNs. A person-years approach will be used as Veterans may be at-risk and eligible for referral for MOUD at multiple time points during the three-year project.

**D.4d2. Implementation/clinical outcomes:** The Quantitative/Economic Core will work with the Implementation Core on two primary areas: (1) ensuring accuracy and consistency of assessments of RE-AIM

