**D.4d3. Analytic approaches:** Our non-randomized evaluation design is necessary because randomization was not possible due to our partnership with VISN leadership and outreach efforts for individual site participation. A key goal is to demonstrate to VISN and facility leadership the value of implementation; therefore, we will estimate implementation outcomes for each of our individual sites and pool implementation sites as appropriate. This will allow us to provide descriptive quantitative information about individual implementation efforts to be combined with qualitative findings about implementation success. Although these analyses will allow for some comparison of effectiveness across individual team efforts, we do not propose formal direct comparisons of teams. There are several statistical limitations to the non-randomized evaluation design that we will address through pragmatic approaches. To account for secular trends in increased use of MOUD that may not be due to our implementation efforts, we will track other related implementation efforts such as initiation of additional SCOUTT efforts, and monitor national dashboards to generate a secular rate among non-intervention sites. We will use this secular rate and test to determine if CONDUIT activities increase use of MOUD above this rate, rather than a null hypothesis of 0. Because we are calculating outcomes for each of the individual sites, the risk of a spurious finding due to multiple testing is possible. We will use caution when interpreting any moderate p-values (e.g. 0.01 to 0.05) as significant. For ease in reporting to VISN and site leadership, we will utilize direct pre- and post-implementation period comparisons. Additional multivariate adjusted analysis using time-to-event semi-parametric methods will also be explored. These models will focus on initiation of MOUD treatment, and will allow for examining clinical and demographic characteristics, including time from initial OUD diagnosis.

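### Table 6 is a one-sample calculation on post-period Veterans only, so its 80% power does not carry over to the direct post-versus-pre comparison when the two periods are independent samples

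*Combined protocol and SAP*

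**What the plan says.** Table 6 in D.4d4 has one index, "Estimated Number of At-Risk Veterans in Post-Implementation Period", with values 50, 75, 200 and 750. Against these it gives effect sizes of 0.40, 0.32, 0.20 and 0.10 at power 0.80. The text concludes that "post-implementation follow-up periods that include samples of 200 patients will allow for detection of meaningful effect sizes in the 0.2 range". It concedes that "Small facilities will have limited power to detect small implementation effects", adds qualitative findings for those sites, and relies on pooling sites with similar strategies for adequate power.

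The comparison itself is set out elsewhere. D.4d1 says: "We will compare outcomes at each implementation site during the post-implementation period to outcomes prior to implementation, using each site as their own control". D.4d3 says that, for reporting to leadership, "we will utilize direct pre- and post-implementation period comparisons". D.4d3 also plans a secular rate from non-intervention sites, and a test of whether CONDUIT activities "increase use of MOUD above this rate, rather than a null hypothesis of 0". For pooled efforts, D.5g plans multilevel models that allow for clustering.

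Table 6 states no test, alpha, sidedness, effect-size metric, pre-period size, patient overlap or intraclass correlation (ICC).

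**The concern.** A post-versus-pre difference carries sampling error from both periods. A table indexed only by post-period Veterans suggests that the pre-period was treated as known. If the two periods are independent samples of similar size, the variance of the difference is twice what a one-sample formula uses, and the stated effects would not be detected with 80% power.

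D.4d3 makes it a key goal to show leadership the value of implementation. If leadership reads a non-significant site-level comparison against a stated 80% power that applies to a different test, it may take the result as failure of facilitation when the comparison was simply less sensitive than stated. The plan already admits weakness at small facilities, so the point bears mainly on the 200 and 750 columns.

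**Working it through.** **Inputs from the documents.** Power 0.80; n = 50, 75, 200, 750; effects 0.40, 0.32, 0.20, 0.10 (Table 6).

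**Assumed, because the plan is silent.** Two-sided alpha 0.05 (the only language on p-values is the caution about 0.01 to 0.05 in D.4d3); effects in SD units; no clustering; pre-period k times the size of the post-period; independence unless stated otherwise.

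**Step 1: reproduce Table 6.** z(0.975) + z(0.80) = 1.960 + 0.842 = 2.802. The one-sample detectable effect is 2.802/√n.

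| n (post) | 2.802/√n | Table 6 | One-sample power at Table 6 effect |
|---|---|---|---|
| 50 | 0.396 | 0.40 | 80.7% |
| 75 | 0.323 | 0.32 | 79.1% |
| 200 | 0.198 | 0.20 | 80.7% |
| 750 | 0.102 | 0.10 | 78.2% |

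All four entries match after rounding. The two-sample formula with n per period gives 0.560, 0.457, 0.280 and 0.145 and matches none. One-sided 0.05 fails too, whether one-sample (0.352, 0.287, 0.176, 0.091) or two-sample with equal periods (0.497, 0.406, 0.249, 0.128).

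**Step 2: add pre-period error.** With independent periods the detectable effect is 2.802 × √((1 + 1/k)/n).

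| k (pre/post) | n = 50 | 75 | 200 | 750 |
|---|---|---|---|---|
| 1 | 0.56 | 0.46 | 0.28 | 0.145 |
| 2 | 0.49 | 0.40 | 0.24 | 0.125 |
| 3 | 0.46 | 0.37 | 0.23 | 0.118 |

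**Step 3: power at the stated effects.** Power = Φ(d × √(n/(1 + 1/k)) − 1.960). For n = 200, d = 0.20, k = 1: 0.20 × √100 = 2.00, and Φ(0.04) = 51.6%.

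- k = 1: 51.6%, 50.0%, 51.6%, 49.1% (noncentral t: 50.8%, 49.5%, 51.4%, 49.0%)
- k = 2: 61-64%
- k = 3: 66-69%
- k = 10: 74-77%

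Reaching 80% takes a pre-period about 52 to 54 times larger in the 50 and 200 columns. The 75 and 750 columns never reach it, because rounding the effect down leaves even the one-sample test at about 78-79%.

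**Step 4: numbers needed.** With equal periods, n per period = 2 × (2.802/d)². For d = 0.20 this is 2 × 14.01² ≈ 393. For 0.40, 0.32 and 0.10 it is about 99, 154 and 1,570.

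**Step 5: other unstated inputs.**

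- *Same Veterans in both periods, effect scaled by the single-period SD.* The variance is 2(1 − f·r)/n, where f is the overlap share and r the within-person correlation. f·r = 0.2 gives 58-61% and 0.4 gives 71-73%; about 0.5 restores the Table 6 figures.
- *Paired, effect scaled by the SD of change.* The formula is 2.802/√n at any correlation, so Table 6 holds.
- *One-sided 0.05, independent.* Equal periods give 61-64%; a pre-period about 3.7 times larger reproduces Table 6.
- *Proportions.* If the effect is an arcsine difference (Cohen's h), with illustrative baselines of 12%, 23.7% and 34%, equal periods give 49-51.5%. The result does not depend on reading the effect as a difference in means.

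**The case against.** **The table may be meant for the secular-rate test.** D.4d3, just before the power section, holds the section's only explicit null value. A one-sample formula indexed by post-period Veterans fits that test if the rate is treated as fixed. This stands, so Table 6 is not miscalculated for every planned analysis. It does not settle the matter. D.4d4 never ties the table to that test, and wording that contrasts the rate with a null of zero can equally describe a test of pre-to-post change, which still carries pre-period error. The direct comparison also remains in the plan.

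**The design may be paired.** D.4d1 describes a cohort tracked over time and notes that "Veterans may be at-risk and eligible for referral for MOUD at multiple time points during the three-year project". With the effect scaled by the SD of change, Table 6 is then correct. This stands as a possibility. Against it, D.4d1 defines at-risk Veterans as having OUD without prescribed MOUD, so those who start and stay on treatment leave the risk set, and strong positive pairing is doubtful for initiation. The documents give no overlap or correlation.

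**Adequate power rests on pooling.** This stands. Reading Table 1 as treated count and treatment rate, the eight listed health systems had about 3,500 untreated Veterans with OUD in Q2 FY19 (for example 139/0.46 − 139 ≈ 163 at Manchester and 173/0.19 − 173 ≈ 738 at Eastern Colorado). That is about nine times 393. These are health-system counts, not participating-clinic counts, and no ICC is given, so pooled power cannot be calculated either way.

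**Cited sources may define the effect size.** The sentence on 200 patients carries two citations that were not available here. They could explain the metric, but Table 6 would still need to name its test.

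A reader might infer that the evaluation has only about 50% power, or that Table 6 contains an arithmetic error. The documents support neither. The entries reproduce exactly under a recognisable formula, and the 49-52% depends on period sizes, independence and alpha that the plan does not state.

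**Conclusion.** The point holds in a limited form. Table 6 contains no pre-period sampling error and no clustering, and the plan does not say which test it serves. For the direct comparison with independent periods, its 80% becomes about 49-52% with equal periods and stays at 74-77% even with a pre-period ten times larger. These figures assume two-sided 0.05 and no clustering. They apply at the tabulated sample sizes only and not to pooled analyses with many more than 200 Veterans, whose power cannot be judged from the documents. Nor does any of these rows give power for the multilevel person-years model with a time interaction in D.5g. This should be corrected; it does not threaten the design.

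**What to change.** 1. Label the existing row of Table 6 *test against a secular rate treated as fixed, no clustering*.
2. Add rows for the direct pre/post comparison, using the expected pre-period size and patient overlap. Until those are known, the Step 2 table gives illustrative rows for independent periods, two-sided 0.05, 80% power and no clustering.
3. State the test, alpha, sidedness and effect-size metric. Inflate any pooled row by a design effect with its assumed ICC, and state the assumed between-period correlation within sites.
4. Limit the sentence on 200 patients to the fixed-rate test. Add that, in a direct pre/post comparison with equal, independent periods, 200 Veterans per period detect about 0.28 with 80% power, and 0.20 needs about 393 per period, before clustering. Present this as an illustration, since D.4d1 allows the same Veteran to appear more than once.
5. Note that the table does not give power for the D.5g models.

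The cost is one table, its assumptions and one or two sentences. The stated detectable effects become less favourable. No added enrolment or design change is needed.

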**D.5. Specific Aim 3. Estimate the cost of implementation and return on investment**

**D.5a. Overview:** We use well-established methods with which our team has extensive experience to estimate the costs of implementation and return on investment with the primary goal of helping VISN leadership evaluate adoption, scale and spread of the clinical programs we implement.

**D.5b. Economic outcomes:** The primary economic outcome across all projects is cost per additional Veteran initiating MOUD. This includes both implementation costs and costs of delivering the clinical program/intervention. Return on investment will also be calculated and will include total costs including concurrent/downstream treatment and medical care costs.

**D.5c. External facilitation costs:** Cost and expenses associated with EF activities will be directly captured through monitoring of expenses associated with QUERI funding as well as VISN contributions. We anticipate that nearly 100% of support from QUERI will be allocated to implementation activities and tracked across the implementation efforts. Efforts that cannot be allocated individually to a specific clinical program (e.g. general interviews with national stakeholders) will be split equally across the relevant EF teams. Implementation staff will be asked to log collateral hours of effort they incur in excess of the QUERI and VISN support. Each month each investigator and project coordinator on the Implementation Core and each EF team will be asked to confirm that the effort allocated to the project (e.g. 10% FTE) and report how those hours were allocated to mutually exclusive implementation activities such as outreach/coordination with sites, planning, training, technical assistance, feedback, evaluation. This effort will be conducted in coordination with the VISN20 Tele-

Pain PII (PI [name]), which is focusing on assessing the implementation costs associated with facilitation of expanding Tele-Pain to CBOCs in Alaska and Oregon. A recent effort by [name] of the QUERI partnered evaluation effort assessing implementation costs associated with the adoption of the Whole Health System of care utilized a similar strategy. A validation step in which implementation activities were re-reviewed with the guidance of a qualitative interviewer found this approach to be robust and reflective of actual implementation effort. Notably, some sites identified costs originally logged as implementation to be reclassified as care delivery activities or other non-related costs of the implementation effort. For this project, we will incorporate brief reviews with key personnel to help ensure appropriate attribution to implementation efforts.

**D.5d. Internal facilitation/site costs:** The Implementation and Quantitative/Economic Cores will rely on parallel efforts to assign costs to implementation efforts at each site, an approach we have refined in our experience with several large projects. In conjunction with the Implementation Core, we will develop items to be included in the monthly implementation log tracking using REDCap. These logs will be completed by sites' internal facilitators to collect data on personnel (e.g. time spent) and non-personnel costs (e.g. travel, supplies, equipment) associated with the implementation efforts. Additional semi-structured interview items capturing personnel time associated with any implementation burdens, as well as items for the 12-month post-implementation survey will also be developed based on the tracking logs and interviews.

**D.5e. Clinical program costs:** In order to identify specific delivery costs of each clinical program, we will utilize a micro-costing approach in which qualitative assessment of providers' time associated with the study is informed by time and motion studies. Process maps of each clinical activity will be generated for each of the five programs. [name] will train internal facilitators to perform time and motion studies as needed to identify estimates of typical times to complete specific program activities. [name] is currently leading the effort to calculate the cost of implementation for the national implementation of the SCOUTT initiative. Methods and tools developed for that evaluation will translate to this work.

**D.5f. Downstream/concurrent costs:** Recent literature has found the additional treatment costs of MOUD are offset by lower utilization of medical services. To calculate the cost offsets associated with MOUD in VHA, we will conduct an ancillary analysis of the cost trajectories between patients treated with and without MOUD. This will be a national analysis to ensure high numbers of MOUD recipients. We will first identify national sample of Veterans eligible for MOUD and the subgroup of those treated with MOUD in 2018. We will extract each patient's healthcare costs using inpatient, outpatient, and pharmacy utilization between 2016 to 2019, which will be used to develop of longitudinal cost trajectories similar to prior work led by Drs. [name] and [name] in the areas of complementary and integrative health. To identify the cost or cost savings attributable to initiation of MOUD, we will compare the costs over time for those patients that are treated with MOUD to those patients that are not treated with MOUD using a difference in differences specification. A generalized gamma regression with log link will be specified. Personnel from HERC are included in the Quantitative/Econ Core to help identify all relevant clinical care costs, as well as to assist in capture all potential utilization activities delivered through community care activities.

**D.5g. Implementation, clinical and cost outcomes analysis:** We will aggregate the personnel time and financial resource data collected to calculate the total cost of IF for each implementation effort. Using an "intent-to-treat" approach with person-years as the unit of analysis, we will calculate separate multilevel mixed models for each clinical/RE-AIM outcome and cost outcome. We will pool implementation efforts across clinical settings as appropriate (e.g. all primary care implementation efforts will be combined into a single analysis). Exposure to IF implementation-as-usual conditions will be based on timing and randomized as appropriate to each project, such as stepped-wedge designs. We will account for clustering of patients across multiple exposure periods, as well as nesting of patients within clinical settings. This approach will allow assignment of at-risk Veterans to different facilitation levels as well as control for secular trends in pre-post implementation efforts. At-risk Veterans who were initially exposed to implementation-as-usual condition will be censored relative to outcome assessment for that phase if they or their provider is exposed to IF. The model will include an indicator variable for implementation and clinic program status, and an interaction between time and this indicator variable to assess for the independent effect of implementation separate of secular trends. Longer term costs, such as 12-month medical care cost trajectories following exposure to potential referral to MOUD will be included as appropriate. Markov models based on the outcome of the point estimates from the clinical and economic outcome models will be developed to estimate confidence intervals of key measures such as cost per additional at-risk patient receiving MOUD.

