### **D.3b. Brief summaries of CONDUIT programs by clinical setting:**

**Primary care:** Buprenorphine delivered in primary care is associated with decreased opioid use, higher quality of care, and improved quality of life. Thus, evidence-based models of primary care-based OUD treatment, namely the Medical Management model and the Nurse Care Management model, are the focus of CONDUIT implementation in primary care settings. In this program, the EF team works collaboratively with internal facilitation teams to expand the availability of MOUD in VHA primary care settings by increasing the number of providers/teams prepared to initiate and manage evidence-based MOUD.

**Specialty care:** This program prioritizes patients on LTOT for chronic pain, as many in this sub-population already have OUD, are at high risk for developing it, or may be experiencing negligible benefit. Consistent with VA/DoD guidelines and a mandate from the Comprehensive Addiction and Recovery Act of 2016, we developed a multi-disciplinary clinical program—the Opioid Reassessment Clinic (ORC)—that assesses benefits and harms, seamlessly initiates MOUD when OUD is diagnosed, and ensures access to evidence-based non-opioid treatments for pain.

**Acute care (inpatient / emergency department):** This program capitalizes on ED visits or hospitalization as critical intervention windows by engaging ED physicians and hospitalists to reduce opioid overprescribing and increase uptake of MOUD while reaching patients at high-risk due to medical comorbidities. We integrate evidence-based and established consensus approaches to opioid prescribing, use of non-pharmacologic pain treatment, and diagnosis and treatment of OUD in hospitalized patients, into a coherent approach that can be adapted to medical centers with and without specialty pain or addiction medicine services.

**Telehealth:** While there is an inadequate number of providers in rural areas certified and/or trained to provide MOUD, telemedicine has been found to be as effective as in-person visits for treating a range of mental illnesses, and for prescribing buprenorphine and other MOUD.

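### The cost-offset analysis targets the effect of starting MOUD but selects everyone treated in 2018, with no new-user rule or index date, which dilutes the estimate toward no effect

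*Combined protocol and SAP*

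**What the plan says.** Section D.5f (downstream/concurrent costs) plans an ancillary national analysis with four elements:

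- **Groups.** "We will first identify national sample of Veterans eligible for MOUD and the subgroup of those treated with MOUD in 2018". The term for eligibility is not defined in this section.
- **Target.** The purpose is stated as "To identify the cost or cost savings attributable to initiation of MOUD". The management plan (G.1) describes the economic work in the same terms, as the savings from initiation.
- **Contrast.** Treated Veterans are compared with "those patients that are not treated with MOUD using a difference in differences specification".
- **Data and model.** Costs come from "inpatient, outpatient, and pharmacy utilization between 2016 to 2019", and "A generalized gamma regression with log link will be specified".

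Section D.5b sets the context. "The primary economic outcome across all projects is cost per additional Veteran initiating MOUD". Return on investment is a separate quantity that "will include total costs including concurrent/downstream treatment and medical care costs".

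**The concern.** A difference in differences learns about starting a treatment only from people who move from untreated to treated inside the data window. A Veteran on MOUD from before 2016 who is still on it in 2018 meets the D.5f definition of treated but never makes that move, so contributes no change from starting. A Veteran who began in 2016 or 2017 and continued has a pre-2018 period that is partly on treatment, so contributes only part of the change. Averaging these Veterans with true starters shrinks the estimate, whether MOUD lowers or raises costs.

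Without an index date the analysis also has no defined before and after for the comparison group. Nor does the section say over what period comparators must be untreated. A comparator who stopped MOUD before 2018 would have a treated early period and would distort the control change in its own right.

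Aim 3 is meant to help VISN leadership judge adoption, scale and spread. If MOUD does reduce other care costs, a diluted offset understates the downstream return. The unit is also mismatched: the rest of Aim 3 counts Veterans who initiate, while this offset would be averaged over initiators and continuing users.

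**Working it through.** **Step 1: is there a new-user rule anywhere?**

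| Feature | Aim 2 (D.4d1, D.4d2) | Cost offset (D.5f) |
|---|---|---|
| Starting population | OUD and not on MOUD | Eligible for MOUD, undefined |
| Index date | Assigned to each at-risk Veteran | None, either group |
| Treatment event | Filling a qualifying prescription | Treated during 2018 |
| MOUD-free look-back | Implied by the cohort definition | None |
| Link to the other section | – | Aim 2 definition not cited |

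D.5g, which describes the outcome models, adds no new-user condition. The plan therefore uses an untreated starting cohort and index dates in Aim 2 and omits both here.

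**Step 2: is there a stated figure to reproduce?** No. D.5f gives no sample size, power or expected effect. What follows is an illustration on assumed inputs.

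**Step 3: dilution under assumptions.** Inputs:

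- True cost ratio from starting MOUD, r: not in the documents; assumed 0.80, 0.90 or 1.10.
- Share p of the treated group on MOUD throughout the pre-period: not in the documents; assumed 0% to 75%.
- Pre-period taken as before 2018. D.5f gives only the 2016 to 2019 extraction window and no cut, so this is an assumption too.
- Same untreated cost (set to 1) for everyone, comparators flat and never on MOUD, and the same r for new and continuing users.

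Formulas:

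- Treated mean before: (1 − p) × 1 + p × r
- Treated mean after: r
- Estimated ratio: r / [(1 − p) + p × r]
- Share of log effect recovered: ln(estimated ratio) / ln(r)

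Worked case, r = 0.80 and p = 50%: before = 0.50 + 0.40 = 0.90; estimate = 0.80 / 0.90 = 0.889; recovered = ln(0.889) / ln(0.80) = 53%.

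| True ratio | p = 0% | p = 25% | p = 50% | p = 75% |
|---|---|---|---|---|
| 0.80 | 0.800 | 0.842 (77%) | 0.889 (53%) | 0.941 (27%) |
| 0.90 | 0.900 | 0.923 (76%) | 0.947 (51%) | 0.973 (26%) |
| 1.10 | 1.100 | 1.073 (74%) | 1.048 (49%) | 1.023 (24%) |

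Percentages are the share of the true log effect recovered. A true 20% saving would appear as 15.8%, 11.1% or 5.9%. With p = 0, the new-user design, the true ratio is returned.

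**Step 4: partly treated pre-periods.** If continuing users spent only a fraction f of the pre-period on MOUD, the treated mean before becomes 1 − p × f × (1 − r), so p × f replaces p. Half the group continuing with half their pre-period treated gives p × f = 0.25 and, for r = 0.80, an estimate of 0.842. The dilution is smaller but in the same direction.

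**The case against.** The best defence is that eligibility in D.5f carries the Aim 2 meaning. D.4d1 defines at-risk Veterans as having OUD without an MOUD prescription, ties that status to eligibility for referral, and expects the harmonised definition to be usable at sites outside the project. Read that way, an eligible Veteran who is later treated is an initiator, and the stated target supports the reading. It is possible, but D.5f neither cites the definition nor sets a baseline date. Without a date, being unprescribed cannot exclude someone treated in 2016 or 2017. An analyst following D.5f as written would include continuing users.

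The second defence concerns stakes, and much of it stands. The analysis is labelled ancillary. The primary economic outcome is built from implementation and programme-delivery costs, so this estimate does not enter it. D.5g separately plans cost models and 12-month cost trajectories, so D.5f is not shown to be the only source for return on investment.

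A third defence is that this is only missing detail. That is too lenient: the selection rule as written does not match the named target, and the remedy is a specific change in who is analysed.

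**Conclusion.** The mismatch between target and treated group is real and should be corrected before the analysis is run. Under the assumptions in the working, its direction is toward no effect. Its size cannot be computed, because the share of continuing users is not given; the ratios of about 0.84, 0.89 and 0.94 for a true 0.80 only show how the dilution behaves. The result bears on the downstream part of return on investment.

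Several stronger conclusions are tempting, and the documents do not support them:

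- **That continuing users dominate.** The VISN rows of Table 1 sum to 2,117 + 833 + 1,554 + 485 = 4,989 Veterans in Q2 FY18 and 2,216 + 863 + 1,701 + 538 = 5,318 in Q2 FY19, a net gain of 329 (6.2% of 5,318). Net gain is starts minus stops. If 10% of the 4,989 had stopped, continuing users would be about 84% of the later count; if 60% had, about 38%. Both fit the same gain. The rows also cover four VISNs at two quarters, not a national 2018 cohort.
- **That no continuing user has an untreated pre-period.** This is strictly true only of those on MOUD since before 2016.
- **That a cost spike before the start inflates the saving.** D.3b says the acute-care programme "capitalizes on ED visits or hospitalization as critical intervention windows", but that describes one of this project's four settings, not how Veterans nationally began MOUD in 2018. A spike is plausible and worth checking; it is not documented.
- **That the gamma model will fail on zero costs.** The cost period is not stated, so zero-cost observations are not established.

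**What to change.** In D.5f:

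1. Define the treated group as Veterans whose first qualifying MOUD record falls in 2018, with none in 2016-2017, and define eligibility explicitly.
2. Require comparison Veterans to be MOUD-free over the same look-back, and state how long afterwards they must remain untreated.
3. Use the first record as the index date for starters and assign comparators a comparable one.
4. Centre costs on the index date, and check that the two groups' cost trends run parallel before it.

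Omitting the quarter before the start from the pre-period is an optional sensitivity analysis. So is a two-part or quasi-Poisson log-link model if zero-cost periods occur.

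The cost is low: a look-back filter and index-date assignment on data already to be extracted for 2016 to 2019, extending the approach used in Aim 2. The treated sample becomes smaller, but the cohort is national and was chosen for its numbers, so it can absorb the loss. No clinical procedure changes.
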